8.6 Duration of cytopenias

The duration of neutropenia and thrombocytopenia will be determined as time from day 1 of treatment until an absolute neutrophil count of 500 or a self-sustained platelet count of 50,000 is reached, respectively. Time to achievement of absolute neutrophil count >1,000/ μ L and platelet count >100,000/ μ L will also be recorded.

8.7 Duration of follow-up

After removal from protocol, patients will be followed to determine event-free survival and disease-free survival (for patients achieving CR or CRi) as well as overall survival (for all patients) for a maximum of 5 years. Follow-up may include periodic (e.g. every 3 months) review of medical records, and, only if absolutely necessary, direct contact of the study participant.

9.0 RECORDS

Research data will be recorded in a study-specific, password protected database using a unique study ID for each patient to assure patient confidentiality. Data from source documents will be transcribed into this database. Source documents are documents where patient data are recorded and documented for the first time. They include, but are not limited to, hospital records, clinical and office charts, laboratory notes, memoranda, quality of life assessments, pharmacy dispensing records, recorded data from automated instruments, copies of transcriptions that are certified after verification as being accurate and complete, X-rays, patient files, and records kept at the pharmacy, laboratories, and medico-technical departments involved in the clinical trial. There will be no case reports forms (CRFs) used for this trial.

The Principal Investigator will ensure that data collected conform to all established guidelines. Each subject is assigned a unique subject number to protect subject confidentiality. Subjects will not be referred to by this number, by name, or by any other individual identifier in any publication or external presentation. The licensed medical records department, affiliated with the institution where the subject receives medical care, maintains all original inpatient and outpatient chart documents. Patient research files will be maintained under control of the Principal Investigator and/or study team and kept in a locked office or file room within a secure building. Access to the study database will be restricted by electronic password protection and restricted access to computers (i.e., locked offices).

10.0 CORRELATIVE STUDIES

Trial participants will be encouraged to participate in correlative studies. From patients who agree to providing biospecimens for correlative research (opt-in/out option in consent form), extra bone marrow and/or peripheral blood specimens will be collected at baseline before initiation of study therapy and at various time points throughout the study when marrow/blood specimens are obtained for routine clinical reasons and then stored in a study-specific sample repository located at Fred Hutchinson Cancer Research Center. See **Appendix C** for instructions on specimen preparation.

11.0 PROTOCOL ENROLLMENT AND SPECIAL CONSIDERATIONS

All eligible patients will be included in this study without regard to gender or ethnicity. The incidence of AML is slightly higher in men, so it is expected that the distribution of these patients will reflect a slight male predominance of the disease as well as the general demographic distribution of AML patients seen at our institution. Based on our statistical approach, we will require no more than 60 patients treated at the MTD to compare with patients treated historically at our institution with GCLAM. Depending on DLTs observed in the phase 1 portion, up to an additional 12 patients may be treated for a maximum possible patient accrual of 72 patients.

Projected Target Accrual ETHNIC AND GENDER DISTRIBUTION CHART

TARGETED / PLANNED ENROLLMENT: Number of Subjects = 72			
Ethnic Category	Sex / Gender		
	Females	Males	Total
Hispanic or Latino	2	4	6
Not Hispanic or Latino	27	39	66
Ethnic Category Total of All Subjects*	29	43	72
Racial Categories			
American Indian/Alaska Native	0	1	1
Asian	2	2	4
Native Hawaiian or Other Pacific Islander	0	0	0
Black or African American	1	3	4
White	25	37	62
Other/More Than One Race/Unknown	0	1	1
Racial Categories: Total of All Subjects*	28	44	72

12.0 GUIDELINES FOR SERIOUS ADVERSE EVENT REPORTING

12.1 Expedited reporting requirements

In accordance with Fred Hutch/UW Cancer Consortium IRB policy, all adverse events (AEs; whether occurring on-site or off-site), which in the opinion of the principal investigator (PI) are (1) unexpected, and (2) related or possibly related to the research, and (3) serious or suggests that the research places research participants or others at a greater risk of physical or psychological harm than was previously known or recognized, will be submitted to the IRB within ten (10) calendar days of learning of the problem. Both the “Expedited Reporting Form for Unanticipated Problems or Noncompliance” and the “Adverse Event Reporting Form”, or equivalent forms, will be completed for this reporting.

12.2 **Definitions**

12.2.1 Adverse event (AE): Any harm or untoward medical occurrence in a research participant administered a medical product, medical treatment or procedure even if it does not necessarily have a causal relationship with the product, treatment, or procedure. An adverse event can be any unfavorable and unintended sign (including an abnormal laboratory finding, for example), symptom, or disease temporally associated with the use of a medical product, medical treatment, or procedure whether or not considered to be related. Mechanisms of obtaining information on AE include monthly transcripts, assessment forms obtained after each clinic visit, and hospital progress and discharge notes. Grade ≥ 3 adverse events other than hematologic toxicities will be recorded, graded, and reported as appropriate. While grade ≥ 3 hematologic AEs are anticipated and are thus not recorded, we will record duration of cytopenias as well as episodes of febrile neutropenia. Medical conditions present before treatment are not AEs and should not be recorded. On the other hand, pre-existing conditions that worsen during treatment will be recorded.

12.2.2 Related or possibly related AE: An AE is “related or possibly related to the research procedures” if in the opinion of the principal investigator, it was more likely than not caused by the research procedures. AEs that are solely caused by an underlying disease, disorder or condition of the subject or by other circumstances unrelated to either the research or any underlying disease, disorder or condition of the subject are not “related or possibly related”. If there is any question whether or not an AE is related or possibly related, the AE should be reported.

12.2.3 Serious AE (SAE): An adverse event that results in any of the following outcomes:

- Death
- Life-threatening adverse event (real risk of dying)
- Prolongation of hospitalization*
- Persistent or significant disability/incapacity/or change in psychosocial status
- Congenital anomaly
- Requires intervention to prevent permanent impairment of damage

*Hospitalization itself will not be considered a serious adverse event if required for complications of AML or comorbid conditions. Hospitalization will be considered a SAE if it fulfills the criteria for a serious and unexpected adverse event as otherwise described.

12.2.4 Unexpected AE: An unexpected adverse event is defined as an event that has a nature or severity, or frequency that is not consistent (a) the known or foreseeable risk of adverse events associated with the research procedures described in the protocol-related documents, such as the IRB-approved research protocol, informed consent document and other relevant sources of information such as product labeling and package inserts; and also are not consistent with (b) the characteristics of the subject population being studied including the expected natural progression of any underlying disease, disorder or condition or any predisposing risk factor profile. with the applicable investigator brochure, or the

prior medical condition of the subject or other treatment given to the subject. “Unexpected,” as used in this definition, refers to an adverse drug experience that has not been previously observed and reported in preclinical or clinical studies rather than an experience that has not been anticipated based on the pharmacological properties of the study drug.

12.3 Grading adverse event severity

All AEs will be graded in severity according to the NCI Common Terminology Criteria for Adverse Events (CTCAE) Version 5.0 (<http://ctep.cancer.gov>). If a CTCAE criterion does not exist, the investigator should use the grade or adjectives: Grade 1 (mild), Grade 2 (moderate), Grade 3 (severe), Grade 4 (life-threatening), or Grade 5 (fatal) to describe the maximum intensity of the adverse event.

12.4 Monitoring, recording, and standard reporting of adverse events

Only grade ≥ 3 adverse events (AEs) other than hematologic toxicities will be recorded, graded, and reported as appropriate per 12.1. AEs will be collected only for the first cycle treatment as detailed in 12.5. If a subject decides to terminate the study early the medical record will continue to be followed for AEs for up to 4 weeks after initial response assessment or a new anti-leukemia therapy is started, whichever occurs first.

Adverse events that do not meet the requirement for expedited reporting will be reported to the IRB as part of the annual renewal of the protocol. Myelosuppression and associated complications are expected events during leukemia therapy; therefore, myelosuppression and associated complications such as fever, infections, bleeding, and related hospitalizations will not be reported as individual AE but will be summarized in the annual report to the IRB.

12.5 Adverse event recording period

AEs will be monitored and recorded in the study database only for the first cycle of therapy since this represents the only experimental therapy. Patients will be monitored from the time of first exposure to the therapy in this study (i.e., the start of the first drug administration infusion on day 0 or day 1) until the start of the second cycle of therapy is initiated, or until 1 month following the initial response assessment, whichever is sooner. AEs with an onset date prior to the first exposure to an investigational product will not be recorded. However, in the case of clinically significant worsening of the AE during the specified AE monitoring time frame, the AE will be recorded.

13.0. DATA AND SAFETY MONITORING PLAN

Institutional support of trial monitoring will be in accordance with the Fred Hutch/University of Washington Cancer Consortium Institutional Data and Safety Monitoring Plan (DSMP). Under the provisions of this plan, Fred Hutch Clinical Research Support (CRS) coordinates data and compliance monitoring conducted by consultants, contract research organizations, or Fred Hutch employees unaffiliated with the conduct of the study. Independent monitoring visits occur at specified intervals determined by the assessed risk level of the study and the findings of previous visits per the institutional DSMP. In addition, protocols are reviewed at least annually and as needed by the Consortium Data and Safety Monitoring

Committee (DSMC), Fred Hutch Scientific Review Committee (SRC) and the Fred Hutch /University of Washington Cancer Consortium Institutional Review Board (IRB). The review committees evaluate accrual, adverse events, stopping rules, and adherence to the applicable data and safety monitoring plan for studies actively enrolling or treating subjects. The IRB reviews the study progress and safety information to assess continued acceptability of the risk-benefit ratio for human subjects. Approval of committees as applicable is necessary to continue the study. The trial will comply with the standard guidelines set forth by these regulatory committees and other institutional, state and federal guidelines.

14.0 INVESTIGATOR OBLIGATIONS

The Principal Investigator (PI) is responsible for the conduct of the clinical trial at the site and is responsible for personally overseeing the treatment of all study subjects. The PI must assure that all study site personnel, including sub-Investigators and other study staff members, adhere to the study protocol and to all applicable regulations and guidelines regarding clinical trials both during and after study completion. All subjects are informed of the nature of the program, its possible hazards, and their right to withdraw at any time, and each subject signs a form indicating their consent to participate prior to receiving any study-related procedures.

15.0 ADMINISTRATIVE AND REGULATORY CONSIDERATIONS

15.1 Protocol interpretation and compliance

The procedures defined in the protocol are carefully reviewed by the PI and his/her staff prior to the time of study initiation to ensure accurate representation and implementation. Protocol amendments, if any, are reviewed and implemented promptly following IRB/EC and relevant Competent Authorities approval.

15.2 Ethical considerations

The Investigator agrees to conduct this study in accordance with applicable United States FDA clinical trial regulations and guidelines, the ICH (E6) GCP guidelines, the IRB/EC and local legal requirements and with the Declaration of Helsinki (1989). The Investigator will conduct all aspects of this study in accordance with all national, state, and local laws of the applicable regulatory agencies.

15.3 Informed consent

The PI and qualified designees assume the responsibility of obtaining written Informed Consent for each subject or the subject's legally authorized representative before any study-specific procedures are performed. Subjects meeting the criteria set forth in the protocol will be offered the opportunity to participate in the study. To avoid introduction of bias, the Investigator must exercise no selectivity with regard to offering eligible subjects the opportunity to participate in the study. Subjects or parents/legal guardians of all candidate subjects will receive a comprehensive explanation of the proposed treatment, including the nature of the therapy, alternative therapies available, any known previously experienced adverse reactions, the investigational status of the study drug, and other factors that are part of obtaining a proper Informed Consent. Subjects will be given the opportunity to ask questions concerning the study,

and adequate time to consider their decision to or not to participate. Informed Consent will be documented by the use of a written Consent Form that includes all the elements required by FDA regulations and ICH guidelines. The form is to be signed and dated by the subject or subject's legally authorized representative and by the person who administers the consent process. A copy of the signed form will be given to the person who signed it, the original signed Consent Form will be filed with the subject's medical records, and copy maintained with the subject's study records. If an amendment to the protocol changes the subject participation schedule in scope or activity, or increases the potential risk to the subject, the Informed Consent Form must be amended. Any amended Informed Consent must be approved by the IRB/EC prior to use. The revised Informed Consent Form must be used to obtain re-consent from any subjects currently enrolled in the study if the subject is affected by the amendment, and must be used to document consent from any new subjects enrolled after the approval date of the amendment.

15.4 Institutional Review Board/Ethics Committee

The PI will assure that an appropriately constituted IRB/EC that complies with the requirements of 21 CFR Section 56 or written assurance of compliance with ICH (E6) guidelines will be responsible for the initial and continuing review and approval of the clinical study. Before initiation of the study, the PI or designee will forward copies of the protocol and Consent Form to be used for the study to the IRB/EC for its review and approval. The PI or designee will also assure that all changes in the research activity and all unanticipated problems involving risks to human subjects or others will be reported promptly to the IRB/EC, and that no changes will be made to the protocol without prior IRB/EC approval, except where necessary to eliminate apparent immediate hazards to human subjects. The Investigator or designee will be responsible for submitting periodic progress reports to the IRB/EC at intervals appropriate to the degree of subject risk involved in the study, but not less than once per year and at the completion or termination of the study.

15.5 Publication statement

The results of this clinical trial may be used for public dissemination in the form of papers, abstracts, posters, or other informational materials to be presented at scientific meetings, or published in professional journals, or as a part of an academic thesis by an investigator. Identifiable patient data may not be used for any of these presentations, manuscripts, or reports unless directed by law.

16.0 STATISTICAL CONSIDERATIONS

16.1 Phase 1 Statistical Considerations

DLTs are defined in Section 8.3. Only DLTs occurring during Cycle 1 will be used to guide dose escalation. However, before the phase 2 portion is begun, all grade 3 and 4 adverse events of all patients treated in the phase 1 portion will be reviewed to assess for late and cumulative toxicities that were not captured during the DLT observation period. The Principal Investigator reserves the right to select a recommended phase 2 dose lower than the MTD if the drug doses identified in the phase 1 portion of this assessment suggest a significant risk of late/cumulative toxicities. Patients will be considered evaluable for DLT if they received at least 75% of the assigned doses of each chemotherapeutic during Cycle 1 or if they developed a DLT.

If a patient does not develop a DLT but does not receive at least 75% of treatment during Cycle 1, the patient will be considered not evaluable for DLT and will be replaced. The dose escalation scheme to define the maximum tolerated dose (MTD).

The dose escalation scheme is as follows:

- A. Evaluate 6 patients at GO1
 - If 0/6 or 1/6 have DLT, change to GO3 and move to (B)
 - If 2 have DLT, declare GO1=MTD and expand cohort to 12 patients and reassess: if $\leq 4/12$ have DLT, proceed with GO1 as MTD, otherwise terminate study, concluding that GO cannot be added to GCLAM chemotherapy.
 - If $\geq 3/6$ have DLT, terminate study, concluding that GO cannot be added to GCLAM chemotherapy.
- B. Evaluate 6 patients at GO3
 - If $\leq 2/6$ patients have DLT, expand cohort to 12 patients and reassess: if $\leq 4/12$ have DLT, move forward with GO3 as MTD; if $>4/12$ have DLT, decrease schedule to GO1, expand GO1 cohort to 12 patients, and reassess: if $\leq 4/12$ have DLT, declare GO1 R2PD. If $>4/12$ have DLT, terminate study.
 - If $\geq 3/6$ have DLT, decrease schedule to GO1, expand GO1 cohort to 12 patients, and reassess: if $\leq 4/12$ have DLT, declare GO1 MTD. If $>4/12$ have DLT, terminate study.

Once the MTD has been determined, all toxicities for all dose levels will be reviewed. If the regimen is considered safe, additional patients be treated at the MTD for the Phase 2 portion of the trial.

16.2 Phase 2 Statistical Considerations

The primary Phase 2 objective will be to evaluate 6-month event-free survival (EFS) at the MTD. EFS will be measured from the date of study registration to the first of: off protocol therapy without a response (morphologic complete remission [CR] with or without measurable residual disease [MRD]; best response of CR without complete count recovery will be considered an event), relapse from a response, or death from any cause with patients last known to be alive without event censored at the date of last contact. The primary endpoints will be 6-month and 1-year EFS (both binary). For the primary endpoints, patients censored before 6 months or 1-year (as appropriate) will be considered a failure. If censoring occurs, secondary analyses analyzing 6-month or 1-year EFS accounting for censoring will be done, including estimating 6-month and 1-year EFS using the Kaplan-Meier method.

Patients treated at the MTD from the Phase 1 portion of the trial will be used in the Phase 2 analysis. Patients with newly-diagnosed AML previously treated at our institution with GCLAM had a 6-month EFS of 68% and 1-year EFS of 60% (null hypothesis). We are interested in whether the proposed regimen can improve 6-month EFS to 81% and/or improve 1-year EFS to 73% (alternative hypothesis).

A two-stage design will be used to evaluate the Phase 2 six-month EFS endpoint. The first stage of the 2 design will evaluate 30 patients. If 20 or more of the first 30 patients are alive without

event at 6-months after study registration, an additional 30 patients will be enrolled. If 46 or more of the 60 patients treated at the MTD are alive and without event at 6-months after study registration, we will consider the regimen of interest for further investigation. If 45 or fewer patients treated that the MTD have an EFS event before 6-months after study registration, we will additionally evaluate 1-year EFS motivated by prior research with GO showing late-emerging benefits of the addition of GO.⁶ If 42 or more patients are alive without event at 1 year, we will consider the regimen of interest for further investigation. Accrual will not be held while waiting for outcome data for the first-stage analysis. This design has a one-sided type-1 error rate of 13% and a power of 95%. Under the null hypothesis of 6-month EFS = 68%, the probability we stop the trial based the first stage evaluation is 35%. Under the alternative hypothesis of 6-month EFS = 81%, the probability we stop accrual after the first stage is 2%. Under the alternative hypothesis, the probability of considering the regimen of interest for further investigation based on 6-month EFS is 84% and under the null hypothesis is 9%.

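### The stated 13% type I error and 95% power do not follow from the decision rule in section 16.2; with 1-year survivors nested in 6-month survivors the exact values are 11.5% and 87.3%

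*Combined protocol and SAP*

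**What the plan says.** All of the relevant text is in section 16.2 of the combined protocol and SAP.

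- **Endpoints.** EFS runs from registration and is read at two landmarks: "The primary endpoints will be 6-month and 1-year EFS (both binary"). On censoring: "For the primary endpoints, patients censored before 6 months or 1-year (as appropriate) will be considered a failure".
- **Hypotheses.** Earlier GCLAM patients "had a 6-month EFS of 68% and 1-year EFS of 60% (null hypothesis"). The aim is to "improve 6-month EFS to 81% and/or improve 1-year EFS to 73% (alternative hypothesis").
- **Rule.** Stage 1 continues if at least 20 of the first 30 patients are event-free at 6 months. The final 6-month test succeeds with at least 46 of 60. If it fails, the 1-year result is examined: "If 42 or more patients are alive without event at 1 year, we will consider the regimen of interest for further investigation".
- **Overall operating characteristics.** "This design has a one-sided type-1 error rate of 13% and a power of 95" per cent.
- **Component figures.** The probability of stopping at stage 1 is given as 35% under the null and 2% under the alternative. The probability of success on 6-month EFS alone is given as 9% and 84%.

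The section does not say how the two endpoints were combined to reach the overall figures, and it does not mention their dependence.

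**The concern.** By the plan's own figures, the 1-year fallback lifts power from 84% to 95%, about 11 points. Only about 14% of trials under the alternative pass stage 1 and then miss 46 of 60, so the fallback would have to rescue roughly three in four of them. That is not plausible. Such a trial has at most 45 patients event-free at 6 months, and to have 42 event-free at 1 year it can lose at most 3 of them in the next six months. Under the alternative, 8/81, or about 10%, of 6-month survivors have an event by 1 year, which is 4 to 5 of 45.

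The sentence at issue is the headline operating characteristic for the two primary endpoints. If it is wrong, a negative trial would be read as having had a 5% chance of missing a regimen that meets both targets when the chance was more than twice that. The fallback, which was added to catch late-emerging benefit, would also be credited with more than it delivers at the design alternative.

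**Working it through.** **Inputs, all from section 16.2.** n = 30 + 30; continue if at least 20; 6-month success if at least 46; otherwise 1-year success if at least 42. Null rates p6 = 0.68 and p12 = 0.60; alternative rates p6 = 0.81 and p12 = 0.73.

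**Step 1: the plan's component figures reproduce.** Let X1 and X2 be independent Bin(30, p6) counts of patients event-free at 6 months in the two stages, and T = X1 + X2.

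| Quantity | Null | Stated | Alternative | Stated |
|---|---|---|---|---|
| P(X1 ≤ 19) | 0.3549 | 35% | 0.0179 | 2% |
| P(X1 ≥ 20 and T ≥ 46) | 0.0935 | 9% | 0.8443 | 84% |
| P(X1 ≥ 20 and T ≤ 45) | 0.5516 | – | 0.1379 | – |

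The rule and rates are therefore being read as the authors read them. The third row is the share of trials that reach the 1-year test.

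**Step 2: the stated overall figures reproduce only under independence.** If the 1-year count is treated as Bin(60, p12) regardless of T, then P(at least 42) is 0.0719 under the null and 0.7520 under the alternative.

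- Null: 0.0935 + 0.5516 × 0.0719 = 0.133
- Alternative: 0.8443 + 0.1379 × 0.7520 = 0.948

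These match 13% and 95%.

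**Step 3: the joint distribution the plan implies.** Each patient has an event (or is censored, which counts as failure) before 6 months, or between 6 and 12 months, or is event-free at 1 year. The two rates in each hypothesis fix all three probabilities, so no correlation has to be assumed. Given T, the 1-year count is Y ~ Bin(T, p12/p6), with p12/p6 = 60/68 under the null and 73/81 under the alternative. Success is X1 ≥ 20 together with T ≥ 46 or Y ≥ 42.

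Given that stage 1 is passed and T ≤ 45, the probability that Y reaches 42 is 0.0392 under the null and 0.2053 under the alternative, against 0.0719 and 0.7520 under independence.

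| | 6-month rule | Added by 1-year rule | Total | Stated |
|---|---|---|---|---|
| Null 68%/60% | 0.0935 | 0.5516 × 0.0392 = 0.0216 | **0.1151** | 13% |
| Alternative 81%/73% | 0.8443 | 0.1379 × 0.2053 = 0.0283 | **0.8726** | 95% |

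Simulation with 2 million replicates agrees to within 0.1 percentage point.

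**Step 4: other readings.**

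- *Stage 1 not enforced* (accrual is not held for the interim): 11.7% and 87.6%.
- *Literal trigger.* The text says "If 45 or fewer patients treated that the MTD have an EFS event before 6-months after study registration", which appears to mean 45 or fewer event-free. Read literally, the results are unchanged: 42 event-free at 1 year implies at least 42 event-free at 6 months, hence at most 18 events by then.
- *The "or" part of the alternative.* Nested power at other 6-month/1-year pairs:

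| Pair | 6-month rule | Added by 1-year rule | Total |
|---|---|---|---|
| 81%/60% | 84.4% | under 0.1% | 84.4% |
| 80%/73% | 79.1% | 4.8% | 83.9% |
| 78%/73% | 66.4% | 11.4% | 77.7% |
| 76%/73% | 52.0% | 21.8% | 73.8% |
| 73%/73% | 31.5% | 39.0% | 70.4% |

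A 1-year rate of 73% with 6-month EFS still at 68% is impossible. With 6-month EFS at 81%, power of 95% needs a 1-year EFS of about 78.6%.

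**The case against.** The arithmetic is not in dispute; the case on the other side concerns weight.

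- **Nothing operational is wrong.** No threshold, sample size or analysis changes, and 13% is a valid upper bound on the type I error. This stands, and it limits the consequence to reporting. It does not make the 95% correct.
- **Sound power figures are already given.** Section 16.2 states 84% for the 6-month test, and section 1.3 states 80% power for an improvement to 80%; the 6-month rule gives 79.1% there. The combined power of 87.3% exceeds both, so the trial is not underpowered on its own terms. This also stands. But the 95% is presented as the power of the whole design, and it is the figure a reader will take away.
- **Some pairs do reach 95%.** With 1-year EFS at 73% and 6-month EFS at 84%, nested power is 95.5%. That needs a rate above a stated target, as does 81%/78.6%, so neither supports 95% at the stated alternative.
- **The late-benefit pairs are not in the protocol.** True; they are illustrations. In particular, 73%/73% assumes no events between months 6 and 12, whereas the plan's null loses 8 points over that interval. The finding rests only on 68%/60% and 81%/73%.
- **The cause is inferred.** Also true. Independence reproduces both figures, but no method is documented. The discrepancy does not depend on the explanation.
- **Precision.** Section 1.3 describes the 60% as a revision after longer follow-up and gives no revised 6-month figure. Whole percentages are therefore enough in the text.

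**Conclusion.** The concern holds. At the plan's own rates and thresholds, the overall type I error is 11.5% rather than 13%, and the power is 87.3% rather than 95%. The chance of discarding a regimen with true 6-month and 1-year EFS of 81% and 73% is 12.7%, about two and a half times the implied 5%. At that alternative the 1-year fallback adds about 3 points of power, not 11. Its contribution grows when the 6-month gain is smaller, but total power is then lower.

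The result assumes independent patients with common event rates, and it uses the nesting that follows from a single EFS clock with censoring counted as failure. It does not depend on whether stage 1 is enforced or on how the trigger sentence is read. The error in the type I figure is conservative; the error in power is not, and it is too large to be rounding.

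**What to change.** In section 16.2, replace the overall type I error with about 12% (11.5%) and the overall power with about 87%. State that these apply at 6-month/1-year EFS of 68%/60% and 81%/73% respectively, and that the 1-year count is drawn from the 6-month survivors, with conditional probabilities 60/68 and 73/81. Optionally, add one figure for a late benefit, such as 78% power at 78%/73%, marked as an illustration.

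The and/or alternative, the thresholds of 20, 46 and 42, and the sample size can all stay. The cost is a wording change to two figures: the stated power becomes less favourable and the stated type I error slightly more favourable.
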